2. STUDY POPULATIONS

- Intent-to-Treat (ITT) population: This population includes all randomized subjects and is the primary population for subject characteristics and all efficacy parameters. All analyses using this population will be based on the treatment to which each subject was randomized.
- As-Treated (AT) population: This population includes all subjects who actually received at least one application of RFA plus ThermoDox (TR) or RFA + dummy infusion (PR). This population will be used for the safety analyses. All analyses using this population will be based on the treatment actually received.

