6.3.2 OS Supportive Analyses

Supportive analyses for OS, conducted in the ITT population (unless otherwise noted), will include:

- a. The unstratified log-rank test and a CPH model (only treatment effect in the model).
- b. Multivariate analysis using the CPH model, including the stratification factors and the following set of potential prognostic/predictive factors: age (< 65 v. \geq 65), race (Caucasian, Asian, Other), region (EU and America, China All, Korea, Other), RFA start time, RFA dwell time (< 90 min, \geq 90 min), device, disease etiology (Hep B, Other), ECOG Performance Status (0, 1, 2, 3, 4, 5), Alfa-feto protein >200 ng/mL (yes/no).
- c. Factors included in the model will be assessed for co-linearity and a stepwise selection process will be applied to identify a final subset of prognostic/predictive factors in the model. Once the subset has been established, treatment will be added to the final model to assess its effect. An exploratory analysis of treatment by factor interactions using the CPH model will be conducted, using the factors identified in the final model above.
- d. Subgroup analyses will also be conducted for the stratification factors and the potential prognostic/predictive factors identified in Section 6.33.b above. The HR and associated 95% CI will be presented for each subgroup.
- e. The primary efficacy analysis, as outlined in Section 6.3.1, will also be run excluding any subjects that met the Major CSR Reportable Protocol Deviation criteria MRD1 to MRD7 as outlined in Section 6.2.2.
- f. A stratified log-rank test using the final strata as recorded on the CRF, in the event there are differences from the primary IVRS assignments. (AT population)
- g. Additional exploratory analyses may be performed.

In addition, a study follow-up Kaplan-Meier analysis (as for OS) will be presented for all subjects. Subjects will be censored if they have died, on their date of death. Only median, 25th and 75th percentiles will be presented.

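### SAP 6.3.2 item f changes population and arm assignment along with the strata, so it may not isolate the effect of stratification errors on OS

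*SAP*

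**What the plan says.** SAP 6.3.1 (and protocol 15.3.2.1) sets the primary OS comparison: a stratified log-rank test in the ITT population, with lesion diameter and RFA route taken from the randomisation assignment.

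SAP 6.3.2 opens with a default: "Supportive analyses for OS, conducted in the ITT population (unless otherwise noted), will include". Item f uses the exception. It specifies "A stratified log-rank test using the final strata as recorded on the CRF", to be run "in the event there are differences from the primary IVRS assignments. (AT population", the closing words being a bracketed population label.

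SAP section 2 fixes what that label means:

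- Arm assignment in ITT: "All analyses using this population will be based on the treatment to which each subject was randomized".
- Arm assignment in AT: "All analyses using this population will be based on the treatment actually received".
- Membership of AT: only subjects who had at least one RFA application together with the ThermoDox or dummy infusion.
- Purpose of AT: "This population will be used for the safety analyses".

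Protocol 15.1 gives the same definitions. SAP 6.3.3 applies the 6.3.2 supportive analyses to PFS, so item f carries over to PFS too.

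**The concern.** Item f is conditional on the CRF strata differing from the randomisation strata. Its purpose is therefore to show whether such discrepancies matter to the OS result. A check of that kind should change the strata and leave the rest of the primary analysis alone.

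As written it can make two further changes: it can drop subjects who were never treated, and it can move subjects who received the wrong treatment into the other arm. If item f then disagrees with the primary result, the strata are only one of three candidate explanations. If it agrees, that does not directly show that the ITT result is robust to corrected strata. Where arms are re-assigned, the comparison is also no longer the one that was randomised.

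What is at stake is the interpretation of one supportive analysis for OS, and of its counterpart for PFS.

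**Working it through.** **1. The plan's own figure.** The event target is 197 deaths for HR 0.67, 80% power, one-sided alpha 0.025 and 1:1 allocation (SAP 6.1.4). Schoenfeld: d = 4(1.960 + 0.842)² / (ln 0.67)² = 196 after rounding up. At 197 deaths the power is 80.2%, ignoring the interim looks. The target reproduces, and item f does not enter it.

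**2. Primary test and item f compared.**

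| Feature | Primary test (SAP 6.3.1) | Item f (SAP 6.3.2 with section 2) |
|---|---|---|
| Source of strata | Randomisation assignment | CRF |
| Subjects | All randomised | Treated only |
| Arm | As randomised | As received |

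Only the first row belongs to the question that item f asks.

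**3. Does another analysis fill the gap?** Item a (ITT) drops stratification altogether. Item d gives hazard ratios within subgroups. Item e repeats the primary method after excluding major deviators. Item g is unspecified. SAP 6.2.1 counts randomisation and stratification errors by arm without re-analysing anything. Protocol 15.3.2.2 has no CRF-strata analysis. So none is listed in ITT.

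**4. Can AT differ from ITT?** Yes, by the plan's own provisions. Randomisation must come at least 24 hours before RFA (protocol 8.1). A subject can fail the temperature criterion immediately before treatment (protocol 6.2.3) or the pre-dose vital-signs check (protocol 10.1.6). Wrong treatment has its own deviation class, RD3 (SAP 6.2.2). These show that a difference is possible; they do not say how common it is.

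**5. Size, on assumed rates.** If 1-3% of randomised subjects are never treated: 550 × 0.01 = 5.5 and 550 × 0.03 = 16.5, or 6-17 subjects. At the average death proportion, 197/550 = 0.358, that is about 2-6 deaths.

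**6. Illustrative simulation (1,500 trials per scenario).** From the plan: 550 subjects, 197 deaths, HR 0.67, control median about 4.5 years, 3% loss per year. Accrual is assumed uniform over the approximately 36 months in the synopsis. Assumed from outside the plan: 25% of lesions above 5 cm, a death hazard ratio of 1.8 for those lesions, and untreated subjects at twice the control hazard. Route was about 9.3% non-percutaneous, following the earlier trial's 90.7% percutaneous, with no route errors. The table shows the standard deviation, across trials, of the change in the log-rank Z.

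| Lesion-size stratum errors | Untreated | Wrong treatment | Strata change alone, in ITT | Further change from switching to AT | Deaths leaving |
|---|---|---|---|---|---|
| 5% | 0% | 0% | 0.11 | 0 | 0 |
| 5% | 1% | 0% | 0.11 | 0.12 | 3.4 |
| 5% | 2% | 0% | 0.11 | 0.16 | 7.0 |
| 5% | 3% | 0.5% | 0.11 | 0.25 | 10.2 |
| 5% | 5% | 1% | 0.11 | 0.33 | 16.9 |
| 2% | 2% | 0.5% | 0.07 | 0.22 | 6.9 |
| 10% | 2% | 0.5% | 0.16 | 0.23 | 6.9 |

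More deaths leave here than in step 5 because untreated subjects were given a doubled hazard. In every scenario with untreated subjects, the unwanted component is at least as large as the one item f is meant to measure, and up to about three times as large. With no untreated or wrongly treated subjects it is exactly zero.

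**The case against.** **AT may equal ITT.** If every subject is treated as assigned, item f isolates the strata effect exactly. A reader might infer that item f can never show what stratum errors do; the documents do not support that, since they give no rate of untreated or wrongly treated subjects. This stands, and it makes the point conditional.

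**Other outputs help.** SAP 6.2.1 reports population sizes, reasons for exclusion and stratification errors by arm, and item a shows whether the ITT result depends on stratification at all. With few discrepant subjects, a difference could be partly traced. It would therefore go too far to say that its cause could never be identified. The help is still partial, because neither output re-runs ITT with corrected strata.

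**There may be a reason for AT.** The RFA route actually used exists only where RFA was performed, so a CRF stratum may be undefined for some subjects. The SAP does not give this reason. It could explain restricting membership, but not analysing by treatment received. Lesion diameter is measured for everyone on the eligibility scan (protocol 12.3).

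**Randomisation is largely preserved.** A reader might infer that item f breaks randomisation outright. The trial is double-blind with dummy premedication and infusion, so non-treatment is less likely to depend on arm, and only wrong-arm treatment moves a subject across. The supportable statement is narrower: when the populations differ, item f is not a comparison as randomised.

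**The consequence is small.** Item f is supportive, conditional and carries no alpha. This also stands.

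**Conclusion.** The point holds in conditional form. Item f combines a change of strata with a change of population and arm assignment. If any randomised subject is untreated or wrongly treated, it may not isolate the effect of stratification errors on OS or PFS. If none is, there is no problem.

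The text comparison needs no assumption. The size does: the 1-3% untreated rate and the non-plan simulation inputs are illustrative, and the absolute movements in Z are modest (standard deviation 0.12 to 0.16 at 1-2% untreated with no wrong treatment). This is a minor, easily corrected weakness in a supportive analysis. Nothing here supports an inference that the primary OS result, its error rate or its power is compromised.

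**What to change.** Reword SAP 6.3.2 item f so that it runs in the ITT population by randomised arm, with these strata:

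- lesion diameter from the CRF for all subjects;
- RFA route from the CRF where RFA was performed, and the randomisation value otherwise.

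The same wording then carries to PFS through SAP 6.3.3. If an AT analysis of OS is wanted, list it as a separate labelled item.

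The cost is one SAP line and one added rule for the RFA route of subjects who had no RFA. That rule leaves their route uncorrected, which is unavoidable. No new data are needed. A difference between item f and the primary test would then reflect the strata alone.

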6.3.3 Secondary Efficacy Variable(s)

PFS will be measured from the date of randomization to the first date on which one of the following occurs, as determined by CT or MRI scan:

- Death of any cause
- Treatment failure (inability to achieve Complete Response (CR) after two RFA \pm ThermoDox treatment sessions)
- Progression due to local tumor recurrence after initial CR

- Progression due to distant intrahepatic tumor recurrence
- Progression due to extrahepatic tumor recurrence

All secondary endpoints comparisons will be made at the 2-sided 0.05 significance level for the ITT population. Since PFS is the only secondary endpoint for regulatory registration purposes, no further multiplicity adjustments will be made. Assuming that OS demonstrates significance at the 1-sided 0.025 level, PFS can subsequently be tested at the 1-sided 0.025 level.

PFS will be analyzed with methodology applied to the OS endpoint. Specifically, PFS will be analyzed with the methodology specified in Section 6.3.1 and the supportive analyses in Section 6.3.2.

In line with FDA guidance (Clinical Trial Endpoints for the Approval of Cancer Drugs and Biologics, 2007), several sensitivity analyses for Progression-Free Survival are also conducted on the ITT Population as follows:

- Analysis that includes clinical progression as a PFS event in addition to the presence of radiological evidence of progression.
- Analysis including clinical progression as a PFS event that also counts initiation of non-study antitumor therapy as an event date rather than as date used to censor subsequent response assessments. (ITT population)
- An analysis that includes all death and response assessments (without censoring missed visits) and also counting as an event, clinical progression, the initiation of anti-tumor therapy or death through the date of cut-off for survival (ITT population)
- Analysis using the next scheduled visit as the event date for radiological progression when image assessment falls more than 1 month after a scheduled assessment. If reassignment of the progression date to the next scheduled visit results in a progression date after death, the death date is used as the event date. (ITT population)
- Kaplan-Meier curves of time to first, second, third, fourth and fifth radiological tumor assessments from date of randomization are done and compared between groups using the log-rank test. (ITT population)

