Data Monitoring Committee	An independent Data Monitoring Committee (DMC) will be established by the Sponsor to review accumulating safety data at regular intervals throughout the study and to monitor trial data integrity. The DMC is responsible for unblinded monitoring of subjects with elevated ($> 2.0 \text{ mg/dL}$ and $\leq 3.0 \text{ mg/dL}$) serum bilirubin levels and will advise if any dose or protocol modification is needed to mitigate risk to such patients. The DMC will also evaluate the results of preplanned interim efficacy and futility analyses for OS. The DMC's specific duties as well as statistical monitoring guidelines and procedures will be fully described in the DMC Charter.
Statistical Methods	OS in the Intent to Treat population will be compared between the two treatment groups using the stratified log-rank test. The estimate of the hazard ratio and corresponding 95% CI will be provided using a Cox proportional hazards (CPH) model including treatment and the stratification factors (maximum lesion diameter [3-5 cm versus $> 5-7 \text{ cm}$] and RFA route [laparoscopic, open surgical, percutaneous]) in the model. The survival curves will be estimated using Kaplan-Meier estimates. PFS will be analyzed using the same methodology.

Sponsor Contact	Celsion Corporation [name] [name] Tel: [REDACTED] Fax: [REDACTED]
-----------------	--

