Post hoc analysis of the PFS and OS data from the HEAT Study suggests that ThermoDox efficacy for the treatment of single lesions is greatly improved when RFA dwell time is \geq 45 minutes. An sRFA treatment for this protocol is defined as the dwell time of \geq 45 minutes measured from the first activation of the RFA probe to produce coagulative necrosis of target tissue through removal of the RFA probe after the final ablation cycle or deployment. This includes the multiple ablation cycles and repositioning time between cycles for an individual patient. Dwell time is relevant for ThermoDox activity because the target tissue and surrounding tissue remain at \geq 40.0°C, even between ablation cycles. This minimum effective dose (MED) of RFA dwell time is achieved by administering 4 ablation cycles. In this trial, all patients will receive the RFA MED of \geq 45 minutes dwell time; in addition, half will be randomized to the ThermoDox MTD of 50 mg/m² and half will be randomized to a dummy infusion of D5W or saline. Randomization and analysis will be stratified by lesion diameter (3-5 cm versus $>$ 5-7 cm) and RFA route (laparoscopic, open surgical, percutaneous). Lesion diameter was found to be a statistically significant prognostic factor in the prior study. Although nearly all subjects in the prior trial (90.7%; 636/701) received percutaneous RFA, this study will also stratify by RFA route for the sake of consistency with the earlier trial's design. Unlike the prior trial, Child Pugh B patients will not be enrolled. They are much more likely than Child Pugh A patients to die from their underlying liver disease, confounding the effect of anticancer treatment (Llovet, et al. 2008). In the HEAT Study, deaths prior to HCC progression occurred at a rate almost five times higher in Child Pugh B patients (19.5%; 8/41) than in Child Pugh A patients (4.1%; 27/660).

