15.5 Interim Analyses

An independent Data Monitoring Committee (DMC) will periodically assess the safety data. A description of the roles and responsibilities and details of the review processes are provided in a separate DMC charter.

Two interim analyses, both for efficacy and futility, are planned for the study. The first is planned after 60% of the target events is reached (118 deaths) and the second after 80% of the events has been reached (158 deaths). The Lan-DeMets alpha-spending approach will be used with O'Brien-Fleming stopping boundaries to evaluate efficacy. Fixed HR boundaries will be used to assess futility. This approach will account for multiple testing and preserve the overall 1-sided study significance level of 0.025. Additional details will be provided in the DMC charter.

No futility analyses are planned during the accrual period. Considering the relative short time of the accrual period compared to the slower accumulation rate of the events, there will not be sufficient events to make such assessment in the accrual study stage.

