6.3 Efficacy Analysis

6.3.1 Primary Efficacy Variable(s)

Overall survival will be measured by time (in months) from randomization to death from any cause or the end of the study. Subjects who have not died will be censored at the date of last study follow-up, or the cut-off date, whichever is earlier as mentioned in Section 3.

The OS cut-off date used for the primary analysis will be based on the observations of the 197th death in the study. All patients dying on the calendar date of the 197th death will be included in the analysis should more than one patient die on the calendar date of the 197th death. Patients having a documented survival status (alive or dead) after this date are censored at the cut-off date.

With the OS cut-off date being event driven, for operational efficiency, the cut-off date for all other study endpoints (e.g., PFS) will be fixed at close proximity of the OS cut-off date, when the milestone is nearing completion. This especially applies to the interim analyses.

OS in the ITT population will be compared between the 2 treatment arms using the stratified log-rank test (Score statistic from PHREG and ties=Breslow (Kalbfleisch and Prentice 1980)). The estimate of the hazard ratio and corresponding 95% CI will be provided using a Cox proportional hazards (CPH) model including treatment and the stratification factors (maximum lesion diameter [3-5 cm versus >5-7 cm] and RFA route [laparoscopic, open surgical, percutaneous]) in the model. The survival curves will be estimated using Kaplan-Meier estimates. The stratification factors will be populated as per the randomization assignment.

Survival for each arm will be summarized using Kaplan Meier curves and is further characterized in terms of the median and survival probability at 12, 24, 36, 48, 60 and 72 months, along with the corresponding 2-sided 95% confidence intervals for the estimates. Confidence intervals for median survival are based upon the methods of (Brookmeyer and Crowley 1982). In addition to Kaplan-Meier estimates, corresponding 2-Sided 95%

confidence intervals constructed using the Clopper-Pearson approximation to the exact binomial proportion (Hollander and Wolfe 1973).

For the first interim analysis, if there are more than 129 events (118+10%), an additional table will be presented for sensitivity purposes, based only on the first 118 events. The same principle applies for the second interim analysis, accordingly.

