6.6 Interim Analysis

Two interim analyses reviewed by the DMC, both for efficacy and futility, are planned for the study. The first is planned after 60% of the target events are reached (118 deaths) and the second after 80% of the events have been reached (158 deaths). The Lan-DeMets alpha-spending approach will be used with O'Brien-Fleming stopping boundaries to evaluate efficacy. Fixed HR boundaries will be used to assess futility. This approach will account for multiple testing and preserve the overall 1-sided study significance level of 0.025. Additional details are provided in the DMC charter.

No futility analyses are planned during the accrual period. Considering the relative short time of the accrual period compared to the slower accumulation rate of the events, there will not be sufficient events to make such assessment in the accrual study stage.

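### PFS is tested at a flat one-sided 0.025 after an OS success that can come at any of three looks; if PFS is tested at that look, its 0.025 is not strictly held, though the excess is small

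*SAP*

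**What the plan says.** SAP 6.3.3 sets a hierarchy: "Assuming that OS demonstrates significance at the 1-sided 0.025 level, PFS can subsequently be tested at the 1-sided 0.025 level". It also says: "Since PFS is the only secondary endpoint for regulatory registration purposes, no further multiplicity adjustments will be made". Protocol 15.3.2.3 carries the same two statements.

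On OS, Protocol 15.5 states: "Two interim analyses, both for efficacy and futility, are planned for the study". The looks are at 118 and 158 deaths, with the final analysis at 197. Efficacy boundaries are of O'Brien-Fleming type with Lan-DeMets spending, and SAP 6.6 says of this: "This approach will account for multiple testing and preserve the overall 1-sided study significance level of 0.025". The looks are counted in deaths, and the synopsis ties the interim efficacy analyses to OS: "The DMC will also evaluate the results of preplanned interim efficacy and futility analyses for OS".

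The PFS data cut is described twice, with a difference. SAP 6.3.1 says that, for operational efficiency, "the cut-off date for all other study endpoints (e.g., PFS) will be fixed at close proximity of the OS cut-off date" and then adds: "This especially applies to the interim analyses". Protocol 15.2.1 defines the OS cut-off for the primary analysis by the 197th death and places the PFS cut-off near it, without the sentence on interims.

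Neither document gives a PFS boundary, a PFS spending function or a planned number of PFS events. Further interim details are left to the DMC charter, which was not available.

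**The concern.** With one analysis, testing PFS at full alpha only after OS succeeds is exact. With three OS looks it is exact only if the PFS analysis time does not depend on the OS result. Under the SAP 6.3.1 wording, PFS may be tested at whichever look OS crosses. Deaths count as PFS events, so the two log-rank statistics are positively correlated. OS then tends to cross at a look where the PFS statistic is also high by chance, and trials that miss early get another chance later. The OS spending function does not protect PFS against this.

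What is at stake is the error rate of the one secondary endpoint named for registration. The case that matters is a true OS effect with no PFS effect.

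**Working it through.** **Inputs from the documents** (SAP 6.1.4 and 6.6): hazard ratio 0.67, power 80%, one-sided 0.025, 1:1 allocation, 550 subjects, looks at 118, 158 and 197 deaths.

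**Assumptions** (the documents give neither): same-look OS-PFS correlation 0.3 to 0.9; PFS information at the two interims from 0.60 and 0.80 up to 0.83 and 0.94 of the final amount.

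**1. The plan's event number.** Schoenfeld: 4 × (1.960 + 0.842)² / (ln 0.67)² = 4 × 7.85 / 0.1604 = 196 deaths, against 197 stated. At 197 deaths the expected OS statistic is 0.4005 × √197 / 2 = 2.81, and Φ(2.81 − 1.96) = 80.2%. With the two interim looks, power is 79.3%. The design figure reproduces.

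**2. OS boundaries.** Spending α(t) = 2 − 2Φ(2.241/√t), where 2.241 is the upper 0.0125 normal point and t is 118/197, 158/197 and 1. This gives z = 2.671, 2.285 and 2.031 (one-sided p = 0.0038, 0.0112, 0.0211).

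**3. Where OS succeeds at hazard ratio 0.67.** At look 1 the expected statistic is 0.4005 × √118 / 2 = 2.175, so the crossing probability is 1 − Φ(2.671 − 2.175) = 0.310. Looks 2 and 3 add 0.290 and 0.193, for a total of 0.793. The interim share is (0.310 + 0.290) / 0.793 = 76%, so an interim crossing is the usual route to OS success.

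**4. PFS error for one test at the look where OS crosses.** The error is the sum over looks k of P(OS first crosses at k and Z_PFS,k > 1.960), with PFS null. It was simulated from the joint normal distribution of the three OS and three PFS statistics.

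| Setting | PFS error |
|---|---|
| Hazard ratio 0.67, whole grid | 0.0239–0.0267 |
| Hazard ratio 0.63, whole grid | 0.0248–0.0263 |
| Maximum over OS effects, correlation 0.3–0.7 | 0.0250–0.0285 |
| Maximum over OS effects, correlation 0.9 | 0.0279–0.0327 |

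The correlation 0.9 maximum occurs near an OS hazard ratio of 0.85, not at the design effect.

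**5. Patient-level model.** This used 550 patients, uniform accrual over 36 months, 3% loss per year and a control median OS of 54 months. PFS was the same in both arms, and the OS effect acted only after progression. Assumed: median PFS of 9, 12 or 24 months, and shared frailty variance 0 or 0.5. With 5% of PFS events being deaths, death before progression occurs in 3.3–4.7% of patients; Protocol 3.3 reports 4.1% (27/660) for HEAT Child-Pugh A patients. The third look falls 28–30 months after the last randomization, in line with the plan's 30. The OS-PFS correlation is 0.23–0.60. PFS error is 0.0233–0.0262 at the design effect and at most 0.0263 over OS effects.

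**6. The two remedies.** In the patient-level model, O'Brien-Fleming-type spending on PFS information, with later looks allowed after OS crosses, has a maximum error of 0.0250–0.0251. One test at the final-look time has the same maximum. Both equal 0.025 within simulation error.

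**The case against.** The strongest reply is that the effect is negligible and may not exist.

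- **The plan may intend a single PFS test.** Protocol 15.2.1 ties the PFS cut to an OS cut-off set by the 197th death, and the synopsis limits interim efficacy analyses to OS. On that reading PFS is tested once, near 197 deaths, with no excess. This stands as one possible reading. The added interim sentence in SAP 6.3.1 leaves the other reading open, so the passages need reconciling.
- **The size rests on inputs the documents do not give.** This stands. In many settings the error is below 0.025; at correlation 0.5 and OS hazard ratios of 0.80–0.85 it is 0.018–0.023. The correlation of 0.9 lies well outside the model's 0.23–0.60.
- **The error case runs against the rationale.** It needs an OS benefit with no PFS benefit, whereas Protocol 3.3 and 6.2.4 describe benefit through better local control. This lowers the practical weight, but strict control has to cover the case.
- **A PFS spending function gives up power.** This is true if it is used for one test only: the error then falls to 0.014–0.017. It does not hold once later looks are allowed (see the fix).
- **The DMC charter may settle it.** It may, but a PFS boundary there would still contradict the SAP statement that no further adjustment is made.

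A reader might infer more than the texts support. Repeated PFS testing at 0.025 at successive looks is planned nowhere; SAP 6.3.1 fixes data cuts, not tests. Nor does the plan lack any confirmatory PFS cut, since Protocol 15.2.1 supplies a candidate. And the OS gate is not broken: on a fair reading, OS significance means crossing the Section 6.6 boundary.

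**Conclusion.** The point holds as a minor one. If PFS is tested at flat 0.025 at the look where OS crosses, the level is not strictly controlled when OS has an effect and PFS has none. At the design hazard ratio the error is about 0.023 to 0.027, an excess of at most about 0.002 and sometimes none. Over all OS effects it is at most about 0.029 for correlation up to 0.7, and 0.033 only at correlation 0.9. If PFS is tested once near the 197th death, there is no excess. The OS error and the 197-death target are unaffected. The sizes depend on assumed OS-PFS correlation, PFS information and, in the patient-level model, median PFS.

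**What to change.** In SAP 6.3.3 and Protocol 15.3.2.3, replace the flat 0.025 for PFS with a separate one-sided 0.025 Lan-DeMets spending function on PFS information. Apply it only from the look at which OS crosses its Section 6.6 boundary, and at later planned looks if needed. State a planned PFS event number. Align SAP 6.3.1, Protocol 15.2.1 and the DMC charter with this.

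**Cost.** A few sentences, plus a PFS event number for which the plan has no assumption yet. The PFS threshold becomes stricter at an interim. In the patient-level model the one-sided p needed is about 0.011–0.017 at the first look, 0.015–0.018 at the second and 0.018–0.019 at the final; if PFS information at the first look were only 0.60, it would be 0.0038. With later looks allowed, overall PFS power is essentially unchanged: in one case (correlation 0.5, PFS information 0.78 and 0.92, one assumed PFS effect) it was 0.670 against 0.667 for the flat rule, with an error of 0.024.

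**Alternative.** State one PFS test at the planned final cut, whichever look OS crosses at. This keeps the full 0.025, but in the same model the PFS claim waits about 17–21 months after an OS success at the first look, or 9–11 months after one at the second.

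Under either option, PFS data gathered after an OS success are investigator-assessed, so the plan should say how assessments stay blinded until the PFS test is done.
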